- 4) Have a lifetime or current diagnosis of Psychotic Disorder as assessed by specified Mini International Neuropsychiatric Interview (MINI) 7.0.2 modules.
- 5) Have a past or current diagnosis of Bipolar Disorder I or II or have a past or current diagnosis of Other specified Bipolar and related disorder as assessed by specified MINI 7.0.2 modules.
- 6) Any otherwise not specified medical or psychiatric condition, illness, disorder, or concomitant medication that could compromise participant safety or treatment, as determined by the Principal Investigator and/or Study Physician.
- 7) Participant considered by the investigator as unsuitable candidate for full participation in the study.

Refer to Table 1 & Table 2 (Prenatal & Postpartum) for the full schedule of assessments, and more details in section AIM 3 and AIM 4 Assessments.

Refer to sections Participant Recruitment (Aim 1, 3, 4), Pre-Screening Assessment (AIM 1, 3, 4), Informed Consent Process (AIM 1, 3, 4), Baseline Screening Phone Visit (AIM 1, 3, 4) for detailed information of the enrollment process.

Aim 4 Approach (Stage IB)

Design The objective of Aim 4 is to conduct a preliminary randomized trial to evaluate the effect of BA on abstinence and depression at 4 ½ months postpartum; to demonstrate the feasibility of the smartphone-delivered BA intervention for depressed pregnant smokers during prenatal and through 2 ½ months postpartum, and feasibility of study procedures. We will recruit pregnant smokers in the same manner as AIM 3 (Stage IA). We will employ a randomized, controlled between groups design in which depressed pregnant smokers will be randomly assigned, using a form of adaptive randomization called minimization,¹¹² to either BA or HW. We will stratify treatment assignment by baseline depression, smoking rate and gestational age. The data that are collected will be used to support feasibility of delivering a prenatal and postpartum intervention to depressed pregnant smokers via smartphone and to provide estimates of effect size for planning future fully-powered trials.

Participants We will recruit up to 50 depressed pregnant smokers who are between 18 to 32 weeks gestational age in their pregnancies.

Compensation AIM 4

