Acceptability of treatment -			x	x	x	x	x	x	x	x	x	x	x	
Acceptability of treatment - Clinician														

(a). MINI Modules: (A, C, D, E, F, G, H, K, N, O)

(b). C-SSRS may be done at any visits as clinically indicated by the Safety Plan

(c). Urine test (cotinine and/or anabasine) will be done at visits where the participant is reporting abstinence and meeting the 7 day point prevalence criteria.

(d). Urine pregnancy test, or if preg test result inconclusive submit paperwork verifying pregnancy

(e). Follow up on any open CCMs/Psychotherapy/Treatments & AEs ONLY

(f). Administer Participant Acceptability of treatment if ppt did not complete at previous timepoints

(g). Clinician Acceptability of treatment may be completed earlier if ppt withdraws from the study

AIM 4: Table 2. Postpartum

Timeline	1 month break after birth of baby	Postpartum Visits (PP)				FU visit
Beginning of Treatment Week		4 visits over 6 weeks				4.5 months from PP
	BIRTH	PP1	PP2	PP3	PP4	FU
Table 2. Screening Assessment Schedule						
Telephone script & screen (basic eligibility)						
Informed Consent verbal/signed						
MINI (a)						
Childhood Trauma Questionnaire						
C-SSRS (b)						
TLFB		x	x	x	x	x
FTND						
Smoking History Form						
Medical History						
Urine Test (urine cotinine and/or anabasine collection) - (c)		x	x	x	x	x
Urine pregnancy test (d)						
Concomitant Medications, Other smoking cessation medications_ treatments & other Psychotherapy		x	x	x	x	x (e)
OUTCOME MEASURES						
PHQ-9		x	x	x	x	x
GAD-7		x	x	x	x	x
NICOTINE WITHDRAWAL						
WSWS-28		x	x	x	x	x
MEDIATORS						
PANAS		x	x	x	x	x
PROMIS Cognitive function-abilities		x	x	x	x	x
OTHER						
Counseling		x	x	x	x	
Adverse Events		x	x	x	x	x (e)
Assessment of Changes since last visit		x	x	x	x	x
FEASIBILITY MEASURES						
WAI-Client Short		x		x		
WAI - Therapist		x		x		
Technical issues questionnaire		x	x	x	x	
Acceptability of treatment -		x	x	x	x	x (f)
Acceptability of treatment - Clinician					x (g)	

(a). MINI Modules: (A, C, D, E, F, G, H, K, N, O)

(b). C-SSRS may be done at any visits as clinically indicated by the Safety Plan

(c). Urine test (cotinine and/or anabasine) will be done at visits where the participant is reporting abstinence and meeting the 7 day point prevalence criteria.

(d). Urine pregnancy test, or if preg test result inconclusive submit paperwork verifying pregnancy

(e). Follow up on any open CCMs/Psychotherapy/Treatments & AEs ONLY

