Rate of recruitment will be calculated as the percentage of eligible participants who are consented to participate.

Retention will be calculated as the percentage of enrolled participants who complete the 4 ½ month postpartum assessments.

Completion of treatment visits will be documented using the participant tracking database. These data will be used to calculate the average number of treatment sessions that participants attend and percentage of participants who complete the prenatal and postnatal treatment protocols.

Completion of study measures will be calculated as the percentage of scheduled assessments completed per visit and percentage of scheduled assessments completed per measure.

Rate of receipt of other smoking cessation, psychopharmacological or psychotherapeutic treatment following enrollment will be recorded in the database.

The rate of technical difficulty with smartphone delivery of treatment and assessments will be calculated as the percentage of treatment and assessment sessions that are interrupted due to technical difficulties with the smart phone.

Verification of pregnancy. Participants will confirm positive pregnancy status through study provided pregnancy test or provide paperwork verifying pregnancy status if the pregnancy test is inconclusive.

Biochemical verification of self-report abstinence will be calculated as the ratio of received urine test results (cotinine and/or anabasine) to number of participants who self-reported abstinence at 4 ½ months postpartum

Acceptability of treatment will be assessed in both participants and therapists (see table of assessments for AIM 4) for timepoints. Participants and therapists will be asked to provide ratings of their satisfaction with the BA and HW interventions. Areas that will be included in these ratings are number of treatment sessions, timing of treatment sessions, and quality of interaction with therapists and study staff (for participants' ratings) and quality of interaction with participants (for therapists' ratings).

Therapeutic alliance will be assessed using the client and therapist-rated Working Alliance Inventory, Short Form at PN2, PN4, PN6, PN8, PN10, PP1 & PP3 visits.¹¹⁶ To maintain boundaries in the therapeutic relationship between therapists and the participants with whom they are working, therapists will not be able to access responses or scores on these instruments. In addition, responses on this instrument will be used in data analyses only.

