Examples of such medical events include allergic bronchospasm requiring intensive treatment in an emergency room or at home, blood dyscrasias or convulsions that do not result in inpatient hospitalization, or the development of drug dependency or drug abuse (21 CFR 312.32).

- Important medical events as defined above may also be considered serious adverse events. Any important medical event can and should be reported as an SAE if deemed appropriate by the Principal Investigator.

- All events occurring during the conduct of a protocol and meeting the definition of a SAE must be reported to the IRB in accordance with the timeframes and procedures outlined in "The University of Texas M. D. Anderson Cancer Center Institutional Review Board Policy for Investigators on Reporting Serious Unanticipated Adverse Events for Drugs and Devices".

- Serious adverse events will be captured from the time of the first protocol-specific intervention, until the last treatment visit, unless the participant withdraws consent. Serious adverse events must be followed until clinical recovery is complete and laboratory tests have returned to baseline, progression of the event has stabilized, or there has been acceptable resolution of the event.

It is the responsibility of the PI and the research team to ensure that serious adverse events are reported according to the Code of Federal Regulations, Good Clinical Practices, the protocol guidelines, the sponsor's guidelines, and Institutional Review Board policy.

STATISTICAL DESIGN AND POWER

We will employ a randomized, controlled between groups design in which 60 depressed pregnant smokers will be randomly assigned, using a form of adaptive randomization called minimization, to either Behavioral Activation (BA) or Health and Wellness (HW). We will stratify treatment assignment by baseline depression, smoking rate, and gestational age.

Data analyses will be conducted by our University of Texas Health Science Center collaborator [name]. [name] will be provided deidentified data from which to conduct the analyses and thus will not have access to participants' protected health information (PHI).

[figure not shown]
General Data Analytic Strategy: Bayesian Statistical Methods

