Simulated Example: As an example of applying a Bayesian analysis, the Figure below depicts the prior and posterior distributions for the probability, and the posterior distribution of the relative risk of smoking abstinence as a function of intervention based on simulated data. Panel A shows the prior and posterior distributions of the absolute probability of treatment initiation as a function of the intervention. The prior distributions (dashed lines) assume that for both intervention conditions all probabilities of smoking abstinence are equally likely (i.e., $\sim\text{Beta}[a=1, b=1]$). The posterior distributions (solid lines) reflect anticipated intervention effects:

1) N= 60 participants randomized in a 1:1 ratio, 2) 7.6% and 25% rates of abstinence at six months post-partum in the control and intervention conditions, respectively (i.e., $\sim\text{Beta}[a=3.28, b=28.72]$ and $\sim\text{Beta}[a=8.5, b=23.5]$ for control and intervention conditions, respectively). Panel B reflects the posterior distribution of the relative risk (calculated directly from the distributions in Panel A (i.e. $p(\text{Abstinence in Intervention})/p(\text{Abstinence in Control})$)) for smoking abstinence. From a Frequentist perspective, this would yield a Fisher Exact $p \leq 0.18$ and relative risk of 2.67 (95% CI 0.78-9.09). (Note: For the Frequentist calculations, to address the non-integer nature of

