Conduct a preliminary randomized trial with depressed pregnant smokers comparing the BA to HW to evaluate the following: 1) The effect of BA on abstinence at 4 ½ months postpartum, which is a primary outcome. Logistic modeling will evaluate smoking abstinence, measured by biochemically verified TLFB, at 4 ½ months postpartum as a function of treatment group. **2) The effect of BA on depression at 4 ½ months postpartum, which is a primary outcome.** Generalized linear modeling will evaluate depression, measured by the PHQ-9, at 4 ½ months postpartum as a function of treatment group. **3) Feasibility of depressed pregnant smokers' acceptance of the smartphone delivery of BA and HW, and assessment components indicated by a) retention, which is a primary outcome, b) completion of prenatal and postpartum sessions, which is a primary outcome c) completion of study assessments, which is a secondary outcome d) strength of therapeutic alliance from both the participant and therapist perspective, which is a secondary outcome and e) participant and therapist ratings on satisfaction questionnaire, which is a secondary outcome.** Survival analysis will evaluate retention by modeling time to drop-out as a function of treatment condition. Binomial logistic modeling will evaluate the proportion of completed sessions as a function of treatment condition across the entire study as well as in the pre-natal and post-partum periods separately. Generalized linear models will evaluate participant and clinician measures of therapeutic alliance, measured by the WAI, as a function of treatment group. Similarly, generalized linear modeling will evaluate satisfaction as a function of treatment group. **4) Feasibility of study procedures as indicated by a) percentage of sessions interrupted by technical difficulties, which is a secondary outcome, and b) percentage of urine tests (cotinine and/or anabasine) received for biochemical verification of self-reported abstinence at 4 ½ months postpartum follow-up, which is a secondary outcome.** Binomial logistic models will evaluate the proportion of sessions interrupted for technical difficulties and the proportion of biochemically verified abstinence measures as a function of treatment. These analyses will provide estimates with 95% credible intervals for each of these proportions in each group that will permit assessment of feasibility.

Specific Analyses: Secondary Aim 1 (Stage IB)

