Evaluate change in hypothesized treatment mechanisms including positive affect, negative affect and cognitive impairment in relation to treatment effects on smoking and depression. It would be ideal to evaluate the change in positive affect, negative affect and cognitive impairment as mediators of treatment effects on 4 ½ month post-partum outcomes via structural equation modeling. Specifically, we could model the change over time in each mediator and evaluate the degree to which each growth factor might transmit the effect of treatment. However, it is possible that a sample size of N = 50 will not provide enough variability to estimate certain parameters implied by such a model (e.g. the slope of change in each of these mediators may have minimal variance and function poorly as a mediator). If this latter scenario obtains, we will evaluate each component of a mediational analysis in separate analyses to evaluate the evidence for mediation of treatment effects by positive affect, negative affect and cognitive impairment. Specifically we will: a) evaluate the change over time in each mediator as a function of treatment using multi-level modeling; b) Evaluate the effect of

treatment on the outcome (smoking cessation or depression); and c) evaluate the outcome (smoking cessation or depression) as a function of change in the mediator captured either through a difference score (six months – baseline) or residual change score (six months residualized on baseline). While the former (SEM) approach would provide a more elegant test of the overall model of behavior change, the latter may be necessary based on the properties of the sample.

PARTICIPANT SAFETY MONITORING PLAN

Assessment of Worsening Depression, Anxiety and Suicide Risk

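### Aim 4 urine-test receipt is assessed per arm on roughly 2 (HW) and 6 to 8 (BA) women at the plan's anticipated rates, too few for the feasibility reading the plan gives the intervals

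*Combined protocol and SAP*

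**What the plan says.** Aim 4, item 4b under Specific Aims, names receipt of urine tests at 4½ months postpartum as an indicator that the study procedures are feasible. Feasibility Measures: AIM 4 defines it: verification "will be calculated as the ratio of received urine test results (cotinine and/or anabasine) to number of participants who self-reported abstinence" at that time point. Specific Data Analyses: Aim 4 repeats the restriction, referring to tests "received for biochemical verification of self-reported abstinence at 4 ½ months postpartum follow-up, which is a secondary outcome". It assigns binomial logistic models by treatment and concludes: "These analyses will provide estimates with 95% credible intervals for each of these proportions in each group that will permit assessment of feasibility".

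Tests are not confined to that visit. Table 2, note (c), says: "Urine test (cotinine and/or anabasine) will be done at visits where the participant is reporting abstinence and meeting the 7 day point prevalence criteria". The table covers the prenatal, postpartum and follow-up visits. For Aim 3 the plan calculates a receipt ratio over sessions 2 to 10; for Aim 4 it defines no corresponding rate across visits.

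The sample size is stated in two ways. The Aim 4 design says "We will recruit up to 50 depressed pregnant smokers", and the mediation section agrees ("it is possible that a sample size of N = 50 will not provide enough variability"). Statistical Design and Power describes a design "in which 60 depressed pregnant smokers will be randomly assigned", and its simulated example has "N= 60 participants randomized in a 1:1 ratio". Both sizes are carried through below.

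**The concern.** The denominator is limited twice: to one visit, and to women who report abstinence at it. In this population the plan expects few such women, above all in HW. A proportion estimated in two women says almost nothing about whether remote verification works, yet the plan tells the reader that the per-arm interval will answer that question. Remote verification underlies the abstinence endpoint of any later trial, so an uninformative answer presented as an assessment could mislead its planning.

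**Working it through.** **1. The plan's own example.** With 30 per arm, a Beta(1,1) prior and rates of 7.6% and 25%, the posteriors are Beta(1 + 2.28, 1 + 27.72) = Beta(3.28, 28.72) and Beta(1 + 7.5, 1 + 22.5) = Beta(8.5, 23.5), as stated. Simulation gives a median relative risk of 2.75 (0.90 to 11.5), against the stated 2.73 (0.90 to 11.44). P(RR > 1) is 96.1% and P(RR ≥ 1.5) is 84.9%, against 96% and 85%. The rates have been read as the plan uses them.

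**2. Expected denominators** (arm size × rate):

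| Assumption | HW | BA |
|---|---|---|
| 25 per arm, 7.6% / 25% | 1.9 | 6.25 |
| 30 per arm, 7.6% / 25% | 2.28 | 7.5 |
| 25 per arm, 9% / 26% (highest depression quartile of the earlier trial, on average 4½ months postpartum) | 2.25 | 6.5 |
| 25 per arm, first row ÷ 0.6 (60% of self-reports verified; assumption) | 3.2 | 10.4 |

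**3. Chance of an empty HW arm.** At a 7.6% self-report rate this is 0.924^25 = 14%, or 0.924^30 = 9%. The chance of at most one woman is 42% or 32%. If self-report is 7.6% / 0.6 = 12.7%, the chance of none at 25 per arm falls to 0.873^25 = 3%.

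**4. Credible intervals for receipt.** These are the 2.5% and 97.5% quantiles of Beta(1 + x, 1 + n − x), using the plan's Beta(1,1) prior for proportions.

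| Received / due | 95% interval |
|---|---|
| 2/2 | 29% to 99% |
| 1/2 | 9% to 91% |
| 3/3 | 40% to 99% |
| 5/6 | 42% to 96% |
| 6/6 | 59% to 100% |
| 8/10 | 48% to 94% |
| 7/8, arms together | 52% to 97% |
| 8/8, arms together | 66% to 100% |

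The plan sets no target for test receipt. If its 70% benchmark for retention and session completion is borrowed as a yardstick, no result in two women excludes 70%, and six of six does not exclude values below it.

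**5. The by-arm logistic model.** If all, or none, of an arm's few tests arrive, the likelihood has no finite maximum for that arm's log-odds. The plan's coefficient prior, Normal with variance 10^4 (SD 100 on the logit scale), restrains it very little, so the prior largely sets the interval. The plan does not say whether this prior or Beta(1,1) governs the per-arm intervals. Step 4 uses the latter.

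**6. What an all-visit rate could add.** Tests from one woman are correlated, so the effective n is W·m / (1 + (m − 1)·ICC) for W women with m requests each. The documents do not fix these inputs. As an illustration only, take W = 10 per arm, close to 25 × 39.2% = 9.8 and 25 × 45.3% = 11.3 from the earlier trial's end-of-treatment abstinence, with m = 6 and 80% receipt.

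- ICC 0.3: 60 / 2.5 = 24.0, interval 60% to 91%.
- ICC 0.5: 60 / 3.5 = 17.1, interval 56% to 92%.
- For comparison, 80% receipt at n = 1.9 gives 19% to 97%, and at n = 6.25 gives 40% to 95%.
- If only the same two HW women contribute, at 14 visits each (PN2 to PN10, PP1 to PP4, follow-up), ICC 0.2 gives 28 / 3.6 = 7.8 and ICC 0.8 gives 28 / 11.4 = 2.5. The intervals are 44% to 95% and 23% to 97%.

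**The case against.** The strongest reply is that the 4½-month restriction is deliberate. Aim 4 asks about that time point because the primary abstinence outcome is measured there, after counseling has ended. Receipt during active counseling is a different quantity and may not carry over. This stands: an all-visit rate can supplement the stated outcome but should not replace it.

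Four stronger readings are tempting, and the documents do not support them.

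- *The plan fixes the denominators at 2 and 6.* The rates come from a simulated example at six months postpartum. The plan's abstinence outcomes require a negative test and count missing as smoking, so self-reporters can outnumber verified abstainers. The test is triggered by a 7-day report, which is easier to meet than prolonged abstinence. Hence the range in step 2.
- *Tests from every other visit are collected and go unused.* Tests are sent only where 7-day abstinence is reported, and those at the end of prenatal and postpartum treatment feed the point-prevalence outcome. Assessment completion is also planned per measure, but as a share of scheduled assessments, which is not clearly receipt among self-reporters.
- *Almost any receipt rate would fit the data.* That is close to true for HW only. With both arms together, eight of eight gives 66% to 100%. Ten of ten in BA, under the 60% assumption, would give 72% to 100%.
- *The trial's feasibility decision is undermined.* The a priori benchmarks concern retention and session completion only.

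It is also fair to say that wide intervals are normal in a pilot. The difficulty is that the plan says these per-arm intervals are sufficient.

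**Conclusion.** The concern holds as a limited point about a secondary outcome. At the anticipated rates, about 2 HW women and 6 to 8 BA women would supply the 4½-month receipt rate. At 50 randomized, about 3 and 10 would do so if 60% of self-reports were verified. The expected per-arm intervals are too wide to judge feasibility, and the HW arm may be empty (9% to 14% at a 7.6% self-report rate, about 3% under the 60% assumption with 25 per arm). This conclusion does not depend on whether 50 or 60 women are randomized. The size of the gain from using other visits cannot be established from the documents. The effective n of about 17 to 24 per arm is an illustration on assumed inputs, and its intervals still span 70%.

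**What to change.** 1. Keep receipt at 4½ months as the stated outcome. Report it as x of y in each arm, and for both arms together with a 95% credible interval.
2. In Specific Data Analyses: Aim 4, drop the by-arm logistic model for this outcome and the statement that its per-arm interval allows feasibility to be judged.
3. In Feasibility Measures: AIM 4 and Specific Data Analyses: Aim 4, add a supplementary rate: tests received divided by tests requested, over all Aim 4 visits where 7-day abstinence was reported and a kit was already in hand. That means visits after PN1, the postpartum visits and follow-up. Urine kits are mailed only after randomization at Visit 1, so counting PN1 would lower the rate artificially.
4. Estimate the supplementary rate for both arms together and by arm, with a random effect for woman, and show treatment visits and follow-up separately.

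Because item 4b keeps its definition, the Specific Aims text need not change. The cost is SAP wording and one clustered analysis, with no new data. The downsides are that receipt during counseling may differ from receipt at follow-up, and that the added precision comes mainly from women who were abstinent earlier. It is small in HW if the same few women supply the tests.
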